6.0 CLINICAL AND LABORATORY EVALUATIONS

6.1 Schedule of Evaluations (SOE)

Evaluation	Screening	Entry/ Day 0	Post-Entry Evaluations									Premature Study Discontinuation ¹ 0/+7
			Day 2	Day 4	Day 6	Day 9	Day 13	Day 17	Day 20	Week 12	Week 24	
Visit Windows (days)			+/-1				+/-2			0/+7	0/+30	
Informed Consent	X											
Documentation of SARS-CoV-2 Result	X											
COVID-19 Symptom Screen	X											
Medical History	X	X										
Medication History	X	X										
Clinical Assessments		X	X	X	X	X	X	X	X	X	X	X
Collect Secondary Contacts Information		X										
Study Kit Dispensed		X										
Dispensing of Study Drug, Confirmation of First Dose, and Counseling		X										
Distribution of Study Diary		X										
Review of Study Diary		X	X	X	X	X	X	X	X			X
Review of Treatment Adherence			X	X	X	X						X
Collection of Study Diary										X		X
Remote Contact		X ²	X	X	X	X	X	X	X	X ²	X	X
Study Endpoint Determination			X	X	X	X	X	X	X	X	X	X
Vital Status Follow-up			X	X	X	X	X	X	X	X	X	X
Household Linkage										X ³		

EVALUATION	Screening	Entry/ Day 0	Post-Entry Evaluations									Premature Study Discontinuation ¹
			Day 2	Day 4	Day 6	Day 9	Day 13	Day 17	Day 20	Week 12	Week 24	
Visit Windows (days)			+/-1				+/-2		0/+7	0/+30		
Self-collected Nasal Swab		X			X				X			X
Nasopharyngeal (NP) Swab		X			X				X			X
Hematology		X			X				X			X
Chemistry		X			X				X			X
Inflammatory Markers		X			X				X			X
Stored Plasma		X			X				X			X
Stored Sera		X			X				X			X
Pharmacokinetics (Sparse)					X				X			X

¹See [Section 6.2.4](#) for specific instructions on evaluations to be performed at the Premature Study Discontinuation visit. Some or all of the evaluations will be performed, depending on the timing of study discontinuation.

²Entry/Day 0 and 20 visits may be in-person or remote for non-sampling subset participants

[^]Household linkage should be assessed after all participants at the site have been enrolled and by the last enrolled participant's Day 20 visit.

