6.2.3 Post-Entry Evaluations

On-Treatment Evaluations

Participants will undergo remote evaluations as outlined in the SOE, [section 6.1](#).

Those participants undergoing additional NP swab, self-collected nasal swab, and blood collection **will be required** to have in-person visits at Days 6 **and** 20.

Post-Treatment Evaluations

Participants will undergo remote evaluations as outlined in the SOE, [Section 6.1](#).

Participants not participating in the sampling subset will undergo **an in-person or remote** study visit on Day 20, as outlined in the SOE, [Section 6.1](#). **Subset participants will have an in-person study visit at Day 20.** The Day 20 visit may occur anytime during the window outlined in the SOE, [Section 6.1](#). For non-subset participants, Day 20 in-person visits should be performed only if the participant has been afebrile for at least 72 hours and other symptoms have improved. If these criteria are not met, the visit should be conducted remotely. **If a remote Day 20 visit is conducted**, arrangements should be made for future transfer of diary **from the participant to the study staff** and provision of compensation for study participation.

Study Completion Evaluations

Participants will undergo a remote evaluation at Week 24.

6.2.4 Discontinuation Evaluations**Evaluations for Participants Who Do Not Start Study Treatment**

Participants who are randomized but do not take the first (confirmed) dose of study treatment do not need to be followed. A study discontinuation eCRF must be completed and any evaluations completed for these participants should also be recorded on the Day 0 eCRFs.

Premature Treatment Discontinuation Evaluations

Participants who discontinue study treatment early should remain on study and all evaluations should be performed as outlined in the [SOE](#).

For participants consenting to the optional intensive sampling study, if the Day 0 CrCl result is <45 mL/min, as calculated by the Cockcroft-Gault equation (see Cockcroft-Gault calculator on the A5395 PSWP), the participant will be prematurely discontinued from study treatment.

Premature Study Discontinuation Evaluations

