Participants who discontinue study participation should undergo premature study discontinuation evaluations, as outlined in the [SOE](#) within 7 days of study discontinuation. If study discontinuation occurs on or prior to Day 7, all procedures should be performed as described in the [SOE](#) for premature study discontinuation evaluations. If study discontinuation occurs on or between Day 8 and Day 20, all evaluations EXCEPT treatment adherence should be performed. If study discontinuation occurs after Day 20, all evaluations EXCEPT treatment adherence, site-collected NP swab, self-collected nasal swab, and blood collection should be performed.

For participants who prematurely discontinue from the study for reasons other than withdrawal of consent, sites will attempt to obtain information regarding vital status and endpoints per the [SOE](#) (see [section 6.3.13](#)).

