10.2.2 Secondary Outcome Measures

- 10.2.2.1 Death from any cause during the 21-day period from and including the day of the first (confirmed) dose of study treatment.
- 10.2.2.2 Death from any cause or hospitalization or urgent visit to an emergency room or clinic during the 21-day period from and including the day of the first (confirmed) dose of study treatment.
- 10.2.2.3 Death from any cause or hospitalization during the 24-week period from and including the day of the first (confirmed) dose of study treatment. Hospitalization is defined as requiring at least 24 hours of acute care in a hospital or similar acute care facility, including Emergency Rooms or temporary facilities instituted to address needs during the COVID-19 pandemic. Evaluation at a hospital or similar facility with less than 24 hours of acute care is not considered a hospitalization.
- 10.2.2.4 Premature discontinuation of study treatment due to an adverse event.
- 10.2.2.5 Occurrence of any cardiac adverse events from start of study treatment through Day 20.
- 10.2.2.6 Duration of fever defined as the last day in the participant's daily diary card on which a temperature greater than 100.4°F was recorded or a potentially antipyretic drug, such as acetaminophen or ibuprofen, was taken.
- 10.2.2.7 Duration of symptoms associated with COVID-19 disease defined as the last day in the participant's daily diary card on which a moderate or worse symptom was recorded. The set of targeted symptoms are the same ones that are used in many influenza studies, with the addition of the symptoms of loss of smell and loss of taste, which have been associated with COVID-19 infection. The symptoms from influenza studies are: cough, shortness of breath, feeling feverish, fatigue, muscle aches, diarrhea, vomiting, nausea, headache, sore throat, nasal obstruction (stuffy nose), and nasal discharge (runny nose). These symptoms are listed individually on the Study Diary that each participant will complete each day. The scoring is that used in influenza studies, whereby participants grade each symptom as absent (score 0), mild (1), moderate (2), or severe (3).
- 10.2.2.8 **Participant-specific area under the curve (AUC) of the symptom**

score associated with COVID-19 disease **over time (through Day 20)** defined as the sum of scores for the targeted symptoms (defined above) in the participant's daily diary record (each individual symptom is scored from 0 to 3).

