10.6.1 Primary Outcome Measure

The cumulative proportion of participants hospitalized or dying during the first 21 days of follow-up will be estimated for each randomized arm, in each risk stratum, using Kaplan-Meier methods to take account of losses to follow-up. For each stratum, the difference between randomized arms in the estimated log cumulative proportion will be calculated and the variance for this difference will be obtained using Greenwood's formula. To compare the outcome in the overall study

population, the stratum-specific estimated differences in log proportion will be combined across strata, weighted by the inverse of the stratum-specific variance of the difference. Two-sided 95% confidence intervals (adjusted for multiple interim analyses), based on this weighted estimator, and associated p-value for the test of no difference between arms will then be obtained.

Participants who prematurely discontinue the study, who are not able to be contacted by the site to ascertain outcomes after discontinuation, will have follow up censored at the date of last known status.

The above analysis assumes that losses to follow-up are non-informative. As a sensitivity analysis of this assumption, causal inference methods, specifically inverse probability of censoring, may be used. These methods may also be used to evaluate the sensitivity of results to crossover of treatment in the placebo arm (i.e., participants taking HCQ and/or Azithro from sources outside of the study).

To evaluate the potential impact of multiple participants enrolling from the same household on the primary inference an additional sensitivity, analysis will restrict to the first person enrolled from each household. If differences are observed, additional considerations will be given to analyses that account for clustering, for example, bootstrap methods to estimate the variance of difference in the primary outcome between randomized arms.

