10.6.2 Secondary Outcomes

The cumulative proportion of participants dying during the first 21 days of follow-up, and through to 24 weeks, and the cumulative proportion hospitalized/dying through to 24 weeks will be analyzed in a similar manner to the primary outcome.

Tolerability (occurrence of premature discontinuation of study treatment due to an adverse event) will be evaluated by estimating the proportion of participants who discontinue study treatment, and will be compared between arms using binary regression with adjustment for a participant's risk stratum. The proportion of participants who experience cardiac adverse events will be analyzed in a similar manner.

Duration of fever, duration of symptoms and duration of time to self-reported return to usual health will be summarized with descriptive statistics. Participant-specific durations of fever and symptoms will be compared between study arms using a two-sided stratified Wilcoxon test with a 5% Type I error rate. Total symptom score will be calculated on each day and the participant-specific area under the curve (AUC) over time will also be compared using a two-sided stratified Wilcoxon test. Participants who do not have complete diary cards due to hospitalization or death will be ranked in these analyses as having poorer outcomes than participants who survived without hospitalization.

The comparison of the proportion of participants with detectable SARS-CoV-2 RNA will use binary regression, with adjustment for risk stratum and pre-treatment SARS-CoV-2 RNA level. The model will be fitted using generalized estimating equations (GEE) to handle the repeated measurements, where the comparison between randomized arms will use a two-sided Wald test. Levels of SARS-CoV2 RNA levels will be compared between arms using non-parametric Wilcoxon rank-sum tests, separately at Day 6 and Day 20, considering results below assay limit as the lowest rank.

Descriptive summaries of clinical outcomes among those hospitalized will be provided by arm, recognizing that this would not be a randomized comparison, if restricted to participants who were hospitalized.

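### Fever and symptom duration score a non-hospitalized participant whose diary stops while still ill as if the illness had ended that day

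*Protocol*

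**What the plan says.** Section 10.2.2.7 makes symptom duration a quantity "defined as the last day in the participant's daily diary card on which a moderate or worse symptom was recorded". Section 10.2.2.6 has the same structure: "Duration of fever defined as the last day in the participant's daily diary card" with a qualifying temperature or use of an antipyretic. Neither definition requires a later well day, and neither has a censoring term.

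Section 10.6.2 fixes the test: "Participant-specific durations of fever and symptoms will be compared between study arms using a two-sided stratified Wilcoxon test". It also gives one rule for incomplete diaries: "Participants who do not have complete diary cards due to hospitalization or death will be ranked in these analyses as having poorer outcomes". The comparison group in that rule is everyone alive and never admitted.

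Section 10.6.1 says that participants who leave the study and cannot be traced "will have follow up censored at the date of last known status". That sentence is written for the primary outcome. Section 10.6.2 carries the primary method over to death and to hospitalization or death, but not to the durations.

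The protocol provides for early exit. Section 6.2.4 states: "If study discontinuation occurs on or between Day 8 and Day 20, all evaluations EXCEPT treatment adherence should be performed".

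**The concern.** Taken together, these rules give a definite value to a diary that stops early in a living, non-hospitalized participant: the last ill day on record. An observation that is really a lower bound on the duration is analysed as the duration itself, and the error always runs toward shorter illness.

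The two outcomes address secondary objective 1.3.3. Under section 10.2 they go into the Primary Analysis Report and the main manuscript, and under section 10.5 the DSMB sees both by arm at each interim review. If one arm has more early stopping, that arm would appear to recover sooner.

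**Working it through.** **Scoring by the text.** Let T be the true last qualifying day and S the day the diary stops. For a non-hospitalized participant the recorded duration is min(T, S).

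- Participant 1: ill to Day 13, diary stops on Day 5. Score 5.
- Participant 2: diary complete, last ill day is Day 10. Score 10.

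Participant 1 gets the better rank although ill for longer. The protocol states no figure for these outcomes that could be reproduced; its 90% power concerns the primary outcome and is not affected.

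**Inputs from the protocol.** About 1,000 per arm (10.4); diary on Days 0-20 (6.3.10); two risk strata (10.3); stratified Wilcoxon test at a two-sided 5% level (10.6.2); hospitalization or death 15% and 10% by arm (10.4 and 10.5), midpoint (15 + 10)/2 = 12.5%.

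**Assumptions, not in the protocol.** No true effect. Equal strata. Lognormal symptom duration with medians 8 and 10 days and log-SD 0.7, capped at Day 20. Hospitalization 7% and 18% by stratum (mean 12.5%), ranked worst. Stop day uniform over Days 1-19. The 5% in section 10.4 is a loss allowance for the primary outcome, not a diary-completion rate, so every stopping rate below is hypothetical.

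**Understatement.** About 48% of stoppers are still ill after stopping. They are scored 6.8 days on average against a true 13.7, so the fall in the mean is roughly (stopping rate) × 0.48 × (13.7 − 6.8):

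- 5% stopping: 0.05 × 0.48 × 6.9 = 0.17 days
- 10% stopping: 0.10 × 0.48 × 6.9 = 0.33 days

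The simulated means, each rounded, are 10.2 days without stopping, 10.0 at 5% and 9.8 at 10%.

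**False rejection by the planned test** (van Elteren form with tie correction, 5,000 simulated trials per row). The last two columns give the z statistic for the stopping imbalance itself: z = (p1 − p2)/√(2p(1 − p)/n), with p the mean of the two rates.

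| Stopping by arm | False rejection | z, 1,000 per arm | z, 250 per arm |
|---|---|---|---|
| 5% vs 5% | 4.7% | 0 | 0 |
| 10% vs 10% | 4.6% | 0 | 0 |
| 6% vs 4% | 5.3% | 2.1 | 1.0 |
| 7.5% vs 2.5% | 8.2% | 5.1 | 2.6 |
| 15% vs 5% | 17.4% | 7.5 | 3.7 |

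For example, 0.05/√(2 × 0.05 × 0.95/1000) = 5.1. The 250 per arm corresponds to the first efficacy review, at about 500 participants. In the last row, 17.3 of the 17.4 points favour the arm that stops more. Repeat runs gave 8.5-9.4% for 7.5% vs 2.5% and 18.4-20.1% for 15% vs 5%.

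**Sensitivity of the planned test.**

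| Scenario | 7.5% vs 2.5% | 15% vs 5% |
|---|---|---|
| Medians 5/7 to 11/13, log-SD 0.5-0.9 | 6.6-10.9% | 9.7-30.0% |
| Fever, medians 3/4 to 5/7 | 5.6-6.6% | 6.7-10.4% |
| Those ill longer than the median twice as likely to stop | 10.3% | 24.0% |

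**Censored alternative.** Stoppers with a qualifying last entry are censored at the stop day. Non-hospitalized participants still ill on Day 20 are placed after all who recovered, and hospitalized or dead participants last. A stratified Gehan-Wilcoxon test on these data rejects 4.9-5.9% in all the cases above (4.6-6.2% in a repeat run).

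With intermittent symptoms, where each earlier ill day qualifies with probability 0.9, 0.7 or 0.5, it gives 4.5-5.4%. The exception is 7.4% at probability 0.5 with 15% vs 5% stopping, where the planned test gives 20.3%.

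**The case against.** The strongest reply is that this is ordinary SAP content. Sections 10.2 and 10.6 send the secondary outcomes to a SAP and call the protocol text an outline aimed mainly at the primary outcome. A SAP could treat a truncated diary as missing or impute it.

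Exposure is also limited. Those who stop treatment are kept in follow-up: "Participants who discontinue study treatment early should remain on study and all evaluations should be performed". That closes much of the most plausible route to unequal stopping, drug intolerance. The schedule lists "Review of Study Diary" at seven post-entry contacts and at premature discontinuation, and diaries can be mailed or sent as images. The DSMB sees losses to follow-up by arm. Material inflation needs something like a threefold imbalance in a double-blind trial, and none is predicted.

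The points on size stand. An imbalance small enough to go unnoticed does little harm, and a large one would show in the DSMB tables if it is recorded as loss to follow-up.

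The deferral to a SAP does not remove the problem. The protocol does not leave the matter open: it fixes the definition, the test and a rule for incomplete diaries, and that rule omits one foreseeable group. Dropping truncated diaries as missing would conflict with section 10.6, which includes every randomized participant who took the first dose. The safeguards make such diaries fewer or visible, but do not change how the remaining ones are scored.

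**Conclusion.** The concern holds. As written, both duration outcomes give too short a value to a non-hospitalized participant whose diary stops while ill. With equal stopping of 5-10% the effect is small: 0.2 to 0.3 days off the mean and no loss of the 5% level. With unequal stopping the comparison is biased toward the arm that stops more, with false rejection of 8.2% at 7.5% vs 2.5% and 17.4% at 15% vs 5% in the base case, and less for fever.

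These sizes rest on assumed symptom courses, stop days and stopping rates; only the direction follows from the text alone. Two secondary outcomes are affected. The primary outcome, the sample size and the stopping boundary are not, and the symptom-score AUC (10.2.2.8) is not part of this point. It should be corrected, and the correction is cheap.

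**What to change.** Amend 10.2.2.6, 10.2.2.7 and 10.6.2 as follows:

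- If a non-hospitalized participant's diary ends before Day 20 with a qualifying entry on the last completed day, treat the duration as censored on that day.
- Order recovered participants by day, place non-hospitalized participants still ill on Day 20 after them, and keep hospitalized or dead participants last.
- Compare arms with a risk-stratified Gehan-Wilcoxon test, which equals a rank test when nothing is censored.
- Report unfinished diaries by arm.
- Show an analysis that ranks early stoppers worse than all non-hospitalized completers only as a bound, because it errs the other way (18.8% false rejection at 15% vs 5%).

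This is wording only; the diary is already recorded daily. For a 10% shorter duration on active treatment with equal stopping, simulated power for the planned test against Gehan-Wilcoxon is 69.2% vs 70.5% at 5% stopping and 67.8% vs 70.5% at 10%. A log-rank test reaches only 44-45% and is not suggested.

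Two limits remain. The analysis assumes non-informative stopping, as section 10.6.1 already does for the primary outcome. A stopper whose last entry happens not to qualify is still counted as recovered.

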HCQ and Azithro have each been used widely for many years, for the independent indications described previously. Potential risks are described further in this section below.

HCQ

Common side effects of HCQ include headache, emesis, diarrhea, vision changes, and muscle weakness. Severe side effects are mainly limited to allergic reactions and eye toxicity, "chloroquine retinopathy" [30], and cardiac toxicity. "Chloroquine retinopathy" is a relatively serious toxicity associated with HCQ use among people taking HCQ for greater than 5 years [31]. Further, rapid-onset retinopathy has been reported in persons being treated with erlotinib and high-dose HCQ (1000 mg daily) for non-small cell lung cancer [32]. Generally, people taking **400** mg of HCQ or less per day or for short periods have a negligible risk of retinopathy, as macular toxicity is related to total cumulative dose [22]. The dose and durations proposed in this trial are unlikely to cause retinopathy [31].

HCQ can prolong the QT interval, and ventricular arrhythmias and TdP have been reported, but usually after prolonged administration [33], particularly in patients with lupus and other comorbidities such as end-stage renal disease [34-37]. **In general**, drug-induced TdP and life-threatening ventricular arrhythmias from HCQ are very rare and typically only observed when doses of 5 g or more are taken [14, 33, 38]. HCQ is a derivative of chloroquine, and the relationship between chloroquine and QT prolongation has been better defined. It is the same molecule that is associated with a prolonged QTc

interval. When chloroquine was administered to healthy adults (regimen 600 mg + 600 mg + 300 mg on Days 1, 2, and 3, respectively) the average increase in QTc interval was 28 ms (18-38 ms; 95% CI) with no cardiac AEs reported [39]. While chloroquine and HCQ are different compounds, animal toxicity studies indicate HCQ is two to three times less toxic across different species [40].

Further, the WHO states, “[d]rug-induced TdP and life-threatening ventricular tachyarrhythmias are very rare events, and there are no simple screening tests to identify people at risk.” Also from WHO, “[d]espite hundreds of millions of doses administered in the treatment of malaria, there have been no reports of sudden unexplained death associated with quinine, chloroquine or amodiaquine, although each drug causes QT/QTc interval prolongation” [38].

Azithro

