Common side effects associated with both oral and IV administration of Azithro include nausea and vomiting, likely due to increased gastric motility [19]. Severe side effects include pseudomembranous colitis, exacerbation of myasthenia gravis, Stevens-Johnson syndrome/toxic epidermal necrolysis, and drug reaction with eosinophilia and systemic symptoms (DRESS) [41, 42]. In addition, there is an increased rate of cancer relapse for hematopoietic stem cell transplant patients with acute lymphocytic leukemia (ALL), acute myelocytic leukemia or bronchiolitis obliterans who received long-term Azithro therapy (greater than 2 years) [43]. However, patients taking Azithro for short periods have a negligible risk of this complication. Azithro crosses the placenta and is found in low concentrations in breast milk, but is considered safe to use in pregnancy [44].

Prolongation of QT with Azithro treatment has been seen in pre-clinical studies, but clinical studies of long term treatment with Azithro have not observed this effect [45]. Additionally, in the preclinical studies that demonstrated QT prolongation with Azithro, the QT prolongation did not lead to TdP, the clinical outcome of concern [24]. Furthermore, in clinical studies of long-term treatment (median of 9 months) with Azithro in patients with non-tuberculous mycobacterial infection, no significant change in QTc intervals and no cardiovascular events were observed during the treatment period [45].

COVID-19

There are some concerning reports that COVID-19 is associated with cardiac disease. In particular, a recent study in China found that persons with underlying cardiovascular disease are at high risk for severe disease and death [46]. It is unclear if cardiac morbidity is worse in the setting of COVID-19 **with** other pneumonia-causing pathogens [47], and unknown if the risks of short course HCQ and Azithro differ in the context of COVID-19.

Assessment of Potential Risks and Benefits

Although there are limited clinical data of HCQ plus Azithro use, there are preclinical data on using chloroquine plus Azithro in a rapid-pacing model in an anesthetized guinea pig model, which has been shown to be predictive of concentration-dependent onset of TdP [48]. This study evaluated increasing doses of azithromycin dehydrate and chloroquine diphosphate given intravenously that achieved clinical use concentrations.

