7.2 Adverse Event Collection Requirements for This Protocol

Post-entry, all AEs must be recorded on the eCRFs within 72 hours if any of the following criteria have been met:

- All Grade ≥ 3 AEs
- All cardiac AEs regardless of grade
- All AEs that led to a change in study treatment/intervention regardless of grade
- All AEs meeting SAE definition or EAE reporting requirement

NOTE: SAEs or events meeting EAE reporting requirements should also be entered into the DAIDS Adverse Experience Reporting System (DAERS), an Internet-based reporting system.

All AEs that are reported must have their severity graded. To grade AEs, sites must refer to the DAIDS AE Grading Table, corrected Version 2.1, July 2017, which can be found on the DAIDS RSC website at <https://rsc.niaid.nih.gov/clinical-research-sites/daims-adverse-event-grading-tables>.

Serious Adverse Events (SAEs)

An SAE is defined as any untoward medical occurrence that:

- Results in death
- Is life-threatening illness
- Requires inpatient hospitalization or prolongation of existing hospitalization
- Results in persistent or significant disability/incapacity
- Is a congenital anomaly/birth defect.
- Is an important medical event that may not be immediately life-threatening or result in death or hospitalization but may jeopardize the patient or may require intervention to prevent one of the other outcomes listed in the definition above).

Ventricular arrhythmias, cardiac events requiring intervention or hospitalization, and deaths should be reported as soon as possible but no later than 24 hours to the A5395 Clinical Management Committee (CMC; e-mail: [contact]). If known, sites should indicate if the death was a sudden cardiac death. Sudden cardiac death is defined in this study as unexpected death from a cardiac cause within 1 hour of onset of symptoms OR found dead without clear explanation.

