8.2 Management of Side Effects of HCQ [78]

Gastrointestinal effects

Gastrointestinal (GI) symptoms including nausea, vomiting, and diarrhea are common with HCQ. HCQ should be administered with food or milk. In the event of GI symptoms, the study staff should review with the participant if HCQ is being taken with food, as administration of HCQ with food may reduce GI effects. GI side effects do not require treatment discontinuation and participants may be referred to their health care provider for symptomatic treatment (e.g., antiemetics). However, in the event of any treatment-related toxicity (GI or other), the site investigator has the option to discontinue study treatment if the side effect is intolerable or at their discretion.

Rash

A range of dermatologic reactions may be observed with HCQ. For pruritus, emollients may be used. For other more significant reactions, such as potential allergic skin reactions, HCQ should be discontinued immediately, and the participant referred to their health care provider or for urgent evaluation and management as appropriate, as determined by the site investigator. Over-the-counter topical agents may be recommended by the site clinical investigator, if the investigator feels able to make such a recommendation.

Hypoglycemia

Severe hypoglycemia (i.e., hypoglycemia that requires intervention) may occur with HCQ. HCQ should be discontinued immediately in participants who develop severe hypoglycemia.

Cardiovascular effects

Cardiomyopathy, QT prolongation, and ventricular arrhythmias have been reported with HCQ use. HCQ should be discontinued immediately in participants who experience a cardiovascular event, and additional evaluation and management pursued as appropriate for the clinical condition, as determined by the site investigator.

In the event of any treatment-related toxicity, the site investigator has the option to discontinue study treatment if treatment is intolerable or at the investigator's discretion. Treatment may be discontinued without contacting the A5395 clinical management committee (CMC) in advance, but the study team should be notified via email within 72 hours of treatment discontinuation, as described above.

Dose modification of HCQ will not be allowed in the study. If HCQ/Placebo is discontinued for toxicity reasons, all study medications should be discontinued and not be restarted.

NOTE: Grades 1 and 2 AEs associated with HCQ require no change in study treatment.

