8.3 Management of Side Effects of Azithro [79]

Hypersensitivity reactions

Allergic reactions such as angioedema, anaphylaxis, Stevens-Johnson syndrome, toxic epidermal necrolysis, and DRESS have been reported rarely with azithromycin

administration. Azithromycin should be discontinued immediately in the event of a hypersensitivity reaction.

Cardiovascular events and altered cardiac conduction

Macrolides have been associated with rare QT prolongation and ventricular arrhythmias but not Azithro in clinical studies (see Rationale above). Some studies, but not all, have described an association between azithromycin and cardiovascular events and mortality [41]. Therefore, to be conservative, Azithro should be discontinued immediately in the event of a cardiovascular event and additional evaluation and management pursued as appropriate for the clinical condition, as determined by the site investigator.

GI symptoms including diarrhea, nausea, and vomiting occur frequently (>10%) in azithromycin recipients. Azithro may be administered with food to reduce GI side effects. GI side effects do not require treatment discontinuation and participants may be referred to their health care provider for symptomatic treatment (e.g., antiemetics). However, in the event of any treatment-related toxicity (GI or other), the site investigator has the option to discontinue study treatment if the side effect is intolerable or at their discretion.

Dose modification of Azithro will not be allowed in the study. If Azithro/Placebo is discontinued for toxicity reasons, all study medications should be discontinued and not be restarted.

NOTE: Grades 1 and 2 AEs associated with Azithro require no change in study treatment.

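### Do the COVID-19 symptom outcomes go wrong by scoring diarrhea, vomiting, nausea and headache, which are also common effects of the study drugs?

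*Protocol*

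**What the plan says.** Protocol 10.2.2.7 measures how long COVID-19 symptoms last: the last diary day with any targeted symptom rated moderate or worse. The targeted set is twelve items taken from influenza studies, among them "cough, shortness of breath, feeling feverish, fatigue, muscle aches, diarrhea, vomiting, nausea, headache, sore throat", plus loss of smell and loss of taste. Each is graded 0 to 3. Outcome 10.2.2.8 sums the same items daily and takes the AUC through Day 20. On recording, 10.2.2.7 states: "These symptoms are listed individually on the Study Diary that each participant will complete each day".

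Section 10.6.2 gives the analysis: "Total symptom score will be calculated on each day and the participant-specific area under the curve (AUC) over time will also be compared", by a two-sided stratified Wilcoxon test, as for duration.

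The safety sections name some of the same symptoms as drug effects:

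- Section 2.1: "Common side effects of HCQ include headache, emesis, diarrhea, vision changes, and muscle weakness"; and "Common side effects associated with both oral and IV administration of Azithro include nausea and vomiting".
- Section 8.2: "Gastrointestinal (GI) symptoms including nausea, vomiting, and diarrhea are common with HCQ".
- Section 8.3: "GI symptoms including diarrhea, nausea, and vomiting occur frequently (>10%) in azithromycin recipients".

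**The concern.** Two outcomes labelled as COVID-19 symptoms include four items that the active regimen is expected to cause. The protocol has no rule for attributing a symptom to drug or disease, and 10.6.2 names only the full set.

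The two outcomes would be affected differently. AUC gains points directly from any drug-caused nausea. Duration changes only if a moderate or worse side effect outlasts every other moderate symptom. In both, a drug-caused excess can only make active treatment look worse, so it could hide a benefit under objective 1.3.3 or look like longer illness.

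The adverse-event record would not fully separate the two. Section 7.2 collects Grade 3 or higher events, cardiac events, SAEs and EAEs, and "All AEs that led to a change in study treatment/intervention regardless of grade". A milder gastrointestinal event that leaves treatment unchanged appears mainly in the diary. The DSMB also sees symptom duration at each interim review (section 10.5).

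**Working it through.** **1. Weight of the overlapping items.** There are 12 + 2 = 14 items, a maximum of 3 points each, and 21 diary days (Days 0 to 20, section 6.3.10).

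- Maximum AUC: 14 × 3 × 21 = 882.
- Four overlapping items: 4 × 3 × 21 = 252, and 252 / 882 = 28.6%.

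The overlap is real. The figure is a share of the theoretical maximum, not of the scores expected.

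**2. Are the four items wrongly placed?** The disease-course text in section 2.1 reports headache or dizziness in 12.1% of COVID-19 cases, diarrhea in 4.8%, and nausea and vomiting in 3.9%. They are therefore disease symptoms by the protocol's own account. Section 10.2.2.7 gives the source of the set (influenza studies plus two COVID-19 additions), and objective 1.3.3 concerns self-reported experience. Nothing here contradicts anything else. Removing the items would discard genuine disease symptoms and any benefit on them.

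**3. What the comparison estimates.** With the full set, the arms are compared on all targeted symptoms that participants report, whatever the cause. If the drugs add nausea, the arms truly differ on that outcome and a rejection is correct. It is an error only relative to another quantity, symptoms caused by the virus alone, which the protocol does not claim to isolate.

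**4. Possible size.** The protocol gives no power or error figure for these outcomes, so there is none to reproduce. It also gives no excess over placebo, severity, side-effect duration or baseline illness. The azithromycin figure of more than 10% has no grade and no comparator. Any size therefore rests on assumptions.

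Assumed inputs:

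- 1000 per arm and two equal risk strata; stratified two-sided Wilcoxon test.
- Hospitalized or dead participants ranked worst (8% in the low-risk and 17% in the high-risk stratum, both arms).
- No drug effect on the illness itself.
- AUC lognormal with mean 60, 90 or 150 and CV 0.6 or 0.8.
- Extra points for an affected participant = symptoms × score 2 × days. One symptom for 2–3 days adds 4–6 points; two symptoms for 5–7 days add 20–28.
- Duration lognormal (log-SD 0.5 or 0.7), capped at Day 20. Affected participants take the larger of their own duration and Day 4 or Day 6, the last azithromycin day and the last full hydroxychloroquine day.

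| Outcome | Assumed excess in active arm | Rejection at nominal 5% |
|---|---|---|
| AUC, one symptom, 2–3 days | 5% or 10% | 5–7% |
| AUC, two symptoms, 5–7 days, mean 60 | 10% | 18–34% |
| same, mean 90 | 10% | 11–19% |
| same, mean 150 | 10% | 8–11% |
| Duration, side effect ends by Day 4, or median illness 8 days or more | 5% or 10% | 4–7% |
| Duration, side effect to Day 6, median illness 5 days | 5% / 10% | 9% / 21% |

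A repeat run agreed with these within simulation error. The average shifts are small. At 10% excess, 28 extra points raise the arm mean by 0.10 × 28 = 2.8, which is 4.7% of a mean of 60 and 1.9% of 150. Six extra points raise it by 0.6, or 0.7% of a mean of 90.

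A separate unstratified simulation with 950 per arm, other baselines, excess up to 20% and side effects lasting to Day 9 gave 4% to 99.9% for duration. That spread shows the documents do not determine the size.

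**5. What else the plan provides.** Duration of fever (10.2.2.6) contains none of the four items. Stopping treatment for an adverse event is its own outcome (10.2.2.4). At each interim review the DSMB sees adverse events and discontinuations with reasons, by arm, beside symptom duration. The efficacy stopping guideline applies to hospitalization or death.

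**The case for a change.** The strongest case for the concern is practical. If the 14-item score is null or adverse, readers will ask whether the drugs failed or simply caused nausea. A reduced-item analysis chosen after unblinding is less convincing than one fixed beforehand. Under the assumptions above, a true 10% lower AUC at mean 90 and CV 0.6 would be detected with 88% power without side effects. With two extra symptoms for 7 days in 10% of the active arm, power is 51%. The DSMB may also look beyond the primary outcome.

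What stands is a caution about interpretation and a reasonable optional analysis. It does not make the protocol wrong. Supportive versions and item summaries by arm are ordinary SAP content. Section 10.2 sends the secondary outcomes to the SAP, and 10.6 calls itself an outline of the main comparisons. The SAP was not available to check, so silence in the outline cannot be read as a decision against such analyses. Because items are stored individually, they can be specified at any time before unblinding without amending the protocol. A reduced score also has its own bias: dropping the items on which harm is expected gives a comparison more favourable to active treatment.

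**Conclusion.** The concern does not hold. The overlap is correctly described (4 of 14 items, 29% of the maximum AUC), but it exposes no wrong number, unsound rule or contradiction. The four items are COVID-19 symptoms in the protocol's own account, and the 14-item outcomes are a defensible measure of net symptom burden. Following the plan as written gives a valid randomized comparison of that quantity.

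The possible influence runs from negligible to material, depending wholly on assumed excess rates, side-effect durations and baseline illness. Its direction is against active treatment, so it cannot create a false claim of benefit, and the primary outcome and sample size are unaffected. Adding reduced-item versions is a matter of preference for the SAP.
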